**7.5 Follow-up of subjects withdrawn from treatment**

Subjects who have withdrawn from the study will be encouraged to report any new symptoms or events that may arise up until withdrawal, enabling prompt medical attention if needed.

**7.6 Premature termination of the study**

The criteria for prematurely terminating the study includes - but are not limited to the following Safety concerns - insufficient or inappropriate device functioning (e.g. when the device produces erroneous measurements that deviate >20% from the golden standard) or regulatory requirements.

## 8. SAFETY REPORTING

### 8.1 Temporary halt for reasons of subject safety

In accordance with section 10, subsection 4 of the WMO, the sponsor will suspend the study if there is sufficient ground that continuation of the study will jeopardise subject health or safety. The sponsor will notify the accredited METC without undue delay of a temporary halt including the reason for such an action. The study will be suspended pending a further positive decision by the accredited METC. The investigator will take care that all subjects are kept informed.

### 8.2 AEs, SAEs and ADEs

#### 8.2.1 Adverse events (AEs)

Adverse events are defined as any undesirable experience occurring to a subject during the study, related to the use of the manual urine monitor or the investigational automated urine monitor FlowSure. All adverse events reported spontaneously by the subject or observed by the investigator, or his staff, during the 24 hour study period will be recorded.

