## 1. INTRODUCTION AND RATIONALE

Diuresis, the amount of hourly produced urine, is a vital parameter that is routinely measured in patients hospitalized patients. Up to half of the millions of patients hospitalized each year in nursing wards and all intensive care unit patients and those undergoing surgery have an indwelling urine catheter inserted into the bladder in order to continuously measure urine production. A reduced diuresis of for example less than 30 millilitres per hour is the first sign of hemodynamic and clinical instability of the patient that can be the result of a (occult) bleeding, infection, or heart failure.

The first response of the body to mitigate hemodynamic instability is to retain fluid by decreasing diuresis. The traditional monitors are insufficient as reading and registering diuresis manually every hour for every patient is burdensome for nurses and often deprioritized due to time constraints. Unlike most other vital parameters, diuresis cannot simply be measured instantly like heart rate or blood pressure but requires monitoring over time which complicates registration. Hourly diuresis registration often is incomplete as nurses are unable to register at set times: a nurse assisting one patient cannot register urine production at the same time of the other patients under his or her watch.

As a result, information about the vital parameter diuresis is often not available when the clinical situation of the patient deteriorates and therefore compromising the patient safety. With accurate and complete information regarding changes in diuresis that prompt automated alerts, a clinical deterioration of the patient's condition will be detected earlier and intervened upon sooner, without an extra burden/time costing intervention of the nurse.

The automated FlowSure monitor is a digital hanging scale that continuously weighs urine production over time, as urine flows through the urine catheter into the catheter bag underneath the patient's bed. FlowSure visualizes the most recent hourly urine production on the screen of the medical device and transmits the generated data to the patient's electronic medical record.

Since the specific weight of urine is equal to water and thus one gram is equal to one millilitre, the increase in weight of the urine bag over time is a surrogate for urine production.

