## 2. OBJECTIVES

The objective of the study is in part A of the study protocol to demonstrate that in clinical care the investigational FlowSure device is able to monitor urine production accurately and safely. The aim in part B of the study is to demonstrate that the use of the investigational FlowSure device will result in more complete and (cost effective) urine production registration.

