#### 8.2.2 Serious adverse events (SAEs)

A serious adverse event is any untoward medical occurrence or effect that:

- results in death
- is life threatening (at the time of the event)
- requires hospitalisation or prolongation of existing inpatients' hospitalisation
- results in persistent or significant disability or incapacity
- is a congenital anomaly or birth defect; or
- any other important medical event that did not result in any of the outcomes listed above due to medical or surgical intervention but could have been based upon appropriate judgement by the investigator.

An elective hospital admission will not be considered as a serious adverse event.

The investigator will report all SAEs to the sponsor without undue delay after obtaining knowledge of the events. The sponsor will report the SAEs in the form of a line listing at least every six months.

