#### 8.2.3 Adverse Device Effects (ADE)

Definition of 'Adverse Device Effect (ADE)': adverse event related to the use of an investigational medical device. This includes any adverse event resulting from insufficiencies

or inadequacies in the instructions for use, the deployment, the implantation, the installation, the operation, or any malfunction of the investigational medical device. This includes any event that is a result of a use error or intentional misuse. Legend for severity of ADE:

- Mild: Minor discomfort noticed but does not interfere with normal daily activity
- Moderate: Discomfort reducing or affecting normal daily activity
- Severe: Incapacitating with inability to work or perform normal daily activity

The sponsor will report expedited the following severe ADE through the web portal

*ToetsingOnline* to the METC:

- Severe ADEs that have arisen in the clinical trial that was assessed by the METC
- Severe ADEs that have arisen in other clinical trials of the same sponsor and with the same medicinal product, and that could have consequences for the safety of the subjects involved in the clinical trial that was assessed by the METC.

The remaining ADEs are recorded in an overview list (line-listing) that will be submitted once every half year to the METC. This line-listing provides an overview of all ADEs from the FlowSure device, accompanied by a brief report highlighting the main points of concern. The sponsor will report expedited all severe ADEs to the competent authorities in other Member States, according to the requirements of the Member States. The expedited reporting will occur not later than 15 days after the sponsor has first knowledge of the adverse reactions. For fatal or life-threatening cases, the term will be maximal 7 days for a preliminary report with another 8 days for completion of the report.

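### Section 8.2.1 makes relatedness to a monitor part of the adverse event definition, so unattributed non-serious events go unrecorded and the AE, SAE and ADE definitions do not fit together

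*Combined protocol and SAP*

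**What the plan says.** Section 8.2.1 sets the definition: an undesirable experience during the study is an adverse event if it is "related to the use of the manual urine monitor or the investigational automated urine monitor FlowSure". The recording rule that follows uses the term so defined: "All adverse events reported spontaneously by the subject or observed by the investigator, or his staff, during the 24 hour study period will be recorded". Section 8.4 requires follow-up until resolution or a stable state for AEs as 8.2.1 defines them. For SAEs it states only that they are reported until the end of the study.

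Section 8.2.2 is worded differently. It opens "A serious adverse event is any untoward medical occurrence or effect that" and lists the seriousness criteria, with no link to a monitor. The reporting duty is equally wide: "The investigator will report all SAEs to the sponsor without undue delay after obtaining knowledge of the events".

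Section 8.2.3 defines an ADE as an "adverse event related to the use of an investigational medical device".

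Safety is a stated aim. Section 2 says Part A should show that FlowSure "is able to monitor urine production accurately and safely", and section 4.3 gives establishing safety as one reason for the 25 patients in Part A. Section 3 describes Part A as single-arm with both devices in use and Part B as randomised without blinding. Section 8.5 provides for no DSMB, and section 11.2 for no formal monitoring. Sections 7.1 and 9 contain no safety endpoint and no safety tabulation.

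**The concern.** Relatedness is normally a second judgement, made on events that have already been written down. Here it is a condition of entry. An event left out on that ground leaves no required record, so the attribution cannot be reviewed later and the excluded events cannot be counted.

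This matters for a hanging scale because its plausible harm is mostly indirect. Section 1 says that a low diuresis "is the first sign of hemodynamic and clinical instability of the patient that can be the result of a (occult) bleeding, infection, or heart failure". A wrong or missing value could delay recognition of such a change, and its early or milder signs are not obviously linked to a scale when they appear. The structured risk analysis (11.7, item c) states that there is no risk of device-related injury because the device does not touch the patient. Staff who share that premise could reasonably class an indirect effect as unrelated. Item i of the same section nevertheless accepts that readings are inadequate if the bag rests on the ground.

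At stake is the completeness of the non-serious safety record, and in Part B an even-handed comparison of that record between arms. Everyone knows which monitor is in use, so the threshold for attribution may differ by arm.

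**Working it through.** The plan states no figure on this point, so none can be reproduced. The check is to apply 8.2.1, 8.2.2, 8.2.3 and 8.4 literally to each kind of event.

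| Event | AE (8.2.1) | ADE (8.2.3) | SAE (8.2.2) | Recorded or reported | Follow-up to resolution (8.4) |
|---|---|---|---|---|---|
| Non-serious, attributed to FlowSure | yes | yes | no | yes | yes |
| Non-serious, attributed to manual monitor | yes | no | no | yes | yes |
| Non-serious, attributed to neither | no | no | no | **no** | **no** |
| Serious, attributed to FlowSure | yes | yes | yes | yes | yes |
| Serious, attributed to manual monitor | yes | no | yes | yes | yes |
| Serious, attributed to neither | **no** | no | yes | yes, as SAE | not stated |

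Three results follow.

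1. *Data are lost in one row only.* A non-serious event attributed to neither monitor meets none of the three definitions, so no rule requires a record of it.
2. *AE and SAE are inconsistent.* In the last row an event is a serious adverse event without being an adverse event. It must be reported, but the duty in 8.4 to follow events until they abate is tied to the 8.2.1 definition and, read literally, does not reach it.
3. *AE and ADE coincide for FlowSure.* The AE set is the union of events related to FlowSure and events related to the manual monitor. Restricting it to events related to the investigational device, as 8.2.3 does, returns every FlowSure AE. The second relatedness step selects nothing, because the wider set it should act on is never collected.

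Exposure: 25 patients in Part A and 25 + 25 in Part B (section 4.3) give 75 patients. At no more than 24 hours each (section 3), that is at most 75 × 24 = 1,800 patient-hours. The documents give neither a background rate of non-serious events nor the share that staff would attribute to a monitor, so the number lost cannot be calculated.

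**The case against.** The strongest reply is section 8.2.2. Bleeding, infection or heart failure with real consequences would normally meet a seriousness criterion and be reported whatever its cause. This stands, and it limits the point to non-serious events.

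Second, the hazard itself, a wrong reading, is measured without any attribution. Part A compares readings with a measuring cup (7.1.1), the move to Part B requires agreement with manual monitoring within 15% (11.7, item e), and deviations above 20% from the reference are a named example of grounds for termination (7.6). This also stands. These checks address accuracy, however, and do not replace a record of what happened to patients.

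Third, in Part A the manual monitor stays in place, so indirect harm from a FlowSure error is less plausible there. This is fair. The mechanism applies mainly to the FlowSure arm of Part B, where the measuring chamber is removed (7.2). Part B in turn aims at completeness of registration, and section 9 plans no comparison of AEs.

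Fourth, the documents do not say who judges relatedness or when. That unblinded staff do so before recording is an inference from the definition and the design, although no masked or independent assessment is described.

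Fifth, a relatedness field would be completed by the same unblinded staff, and an all-cause list in ward and cardiac care patients would be mostly background illness. Both statements are true. The gain is that the unattributed events stay on record and can be counted by arm or reassessed.

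Sections 7.5 and 10.3 show interest in new symptoms and complications generally, but neither sets a rule for recording them.

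**Conclusion.** The point holds for non-serious events. As written, 8.2.1 leaves those not attributed to a monitor unrecorded and without follow-up under 8.4, in an unblinded first-in-human study meant in part to establish safety. It also leaves 8.2.1, 8.2.2 and 8.2.3 inconsistent with one another. This rests on reading the definition literally and on the recording rule using the term as defined. The size of the loss is unknown. It is a modest defect of wording and data collection, and no figure in the plan changes.

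A reader might infer two stronger conclusions that the documents do not support. One is that the safety objective rests only on events filtered by attribution. It does not, because all SAEs are reported regardless of cause and accuracy is measured against a reference. The other is that the Part B arms cannot be compared for safety. All-cause SAEs can be compared by arm; only the comparison of non-serious events is exposed to differential attribution.

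**What to change.** - In 8.2.1, delete the clause that ties an AE to either monitor, and record every undesirable experience during the patient's study period of at most 24 hours. SAEs then become a subset of AEs, and the follow-up rule in 8.4 covers both.
- Add one case report form field for relatedness: FlowSure, manual monitor, or not related. State the assessor's role and the criteria used.
- Derive the ADE list in 8.2.3 from that field.
- Add to section 9 a descriptive table of AEs and SAEs for Part A and by arm for Part B. No test is needed.

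The cost is a change of wording, one field and one table. The downside is more non-serious entries, mostly background illness, in 75 patients over at most 24 hours each. The field does not remove unblinded judgement, but it keeps that judgement visible and separate from the decision to record.

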#### 8.2.2 Serious adverse events (SAEs)

A serious adverse event is any untoward medical occurrence or effect that:

- results in death
- is life threatening (at the time of the event)
- requires hospitalisation or prolongation of existing inpatients' hospitalisation
- results in persistent or significant disability or incapacity
- is a congenital anomaly or birth defect; or
- any other important medical event that did not result in any of the outcomes listed above due to medical or surgical intervention but could have been based upon appropriate judgement by the investigator.

An elective hospital admission will not be considered as a serious adverse event.

The investigator will report all SAEs to the sponsor without undue delay after obtaining knowledge of the events. The sponsor will report the SAEs in the form of a line listing at least every six months.

#### 8.2.3 Adverse Device Effects (ADE)

Definition of 'Adverse Device Effect (ADE)': adverse event related to the use of an investigational medical device. This includes any adverse event resulting from insufficiencies

or inadequacies in the instructions for use, the deployment, the implantation, the installation, the operation, or any malfunction of the investigational medical device. This includes any event that is a result of a use error or intentional misuse. Legend for severity of ADE:

- Mild: Minor discomfort noticed but does not interfere with normal daily activity
- Moderate: Discomfort reducing or affecting normal daily activity
- Severe: Incapacitating with inability to work or perform normal daily activity

The sponsor will report expedited the following severe ADE through the web portal

*ToetsingOnline* to the METC:

- Severe ADEs that have arisen in the clinical trial that was assessed by the METC
- Severe ADEs that have arisen in other clinical trials of the same sponsor and with the same medicinal product, and that could have consequences for the safety of the subjects involved in the clinical trial that was assessed by the METC.

The remaining ADEs are recorded in an overview list (line-listing) that will be submitted once every half year to the METC. This line-listing provides an overview of all ADEs from the FlowSure device, accompanied by a brief report highlighting the main points of concern. The sponsor will report expedited all severe ADEs to the competent authorities in other Member States, according to the requirements of the Member States. The expedited reporting will occur not later than 15 days after the sponsor has first knowledge of the adverse reactions. For fatal or life-threatening cases, the term will be maximal 7 days for a preliminary report with another 8 days for completion of the report.

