### 8.3 Annual safety report

In addition to the expedited reporting of severe ADEs, the sponsor will submit, once a year throughout the clinical trial, a safety report to the accredited METC, competent authority, and competent authorities of the concerned Member States.

This safety report consists of:

- a list of all suspected (unexpected or expected) severe adverse device events, along with an aggregated summary table of all reported serious adverse reactions, ordered by organ system, per study

- a report concerning the safety of the subjects, consisting of a complete safety analysis and an evaluation of the balance between the efficacy and the harmfulness of the medicine under investigation.

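### Expedited reporting of device effects is triggered by intensity rather than seriousness, so a serious effect graded mild or moderate reaches the METC only on a half-yearly list

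*Combined protocol and SAP*

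**What the plan says.** Three parts of Section 8 bear on this.

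- **8.2.2** defines a serious adverse event by outcome: death, threat to life, hospitalisation or a longer stay, disability, congenital anomaly, or another important medical event. The investigator must tell the sponsor promptly of every SAE. The sponsor's onward duty is periodic: "The sponsor will report the SAEs in the form of a line listing at least every six months".
- **8.2.3** gives ADEs a three-step intensity legend. The top two steps are "Moderate: Discomfort reducing or affecting normal daily activity" and "Severe: Incapacitating with inability to work or perform normal daily activity". The reporting rule follows directly: "The sponsor will report expedited the following severe ADE through the web portal". Its first listed item is "Severe ADEs that have arisen in the clinical trial that was assessed by the METC", and the duty to authorities elsewhere uses the same word: "The sponsor will report expedited all severe ADEs to the competent authorities in other Member States". Everything else is covered by this sentence: "The remaining ADEs are recorded in an overview list (line-listing) that will be submitted once every half year to the METC". Expedited reports are due within 15 days. For fatal or life-threatening cases, a preliminary report is due within 7 days, with 8 more to complete it.
- **8.3** asks for "a list of all suspected (unexpected or expected) severe adverse device events" in the annual safety report, and in the same item for a summary table of *serious* adverse reactions.

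**The concern.** Severity (how intense an event is) and seriousness (what it leads to) are different attributes, and the protocol defines both. The expedited rule is attached to the first. An event can be serious under 8.2.2 without being incapacitating.

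The gap is plausible for this device. FlowSure does not touch the patient (11.7 c), so any harm is likely to come through a wrong or missing reading. The ADE definition in 8.2.3 covers malfunction and use error, and 11.7 (i) accepts that readings are inadequate if the bag touches the ground. Section 1 treats a fall in diuresis as an early sign of instability, and in Part B the device replaces the manual monitor (7.2). As an illustration, a missed fall in diuresis that lengthened the stay would be serious under 8.2.2, yet might cause no discomfort that a grader would attribute to the device.

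At stake is how soon a body outside the study team sees such an event. The trial is first-in-human (4.3, 6.2), has no DSMB (8.5) and no formal monitoring (11.2), so event-level reporting to the METC is one of the few external checks.

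**Working it through.** The plan gives no statistical figure to reproduce. The check is to follow each combination of seriousness and severity through the rules as written.

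| ADE | Route from sponsor to METC | Latest arrival |
|---|---|---|
| (a) serious and severe | expedited under 8.2.3 | 15 days (7 + 8 if fatal or life-threatening) |
| (b) severe, not serious | expedited under 8.2.3 | 15 days |
| (c) serious, mild or moderate | half-yearly ADE list (8.2.3); SAE line listing (8.2.2) | about 6 months |
| (d) neither | half-yearly ADE list (8.2.3) | about 6 months |

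The 15-day limit is taken to cover expedited reports to the METC as well as to authorities in other Member States; the sentence is general but follows the one on Member States.

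**Size of the gap in (c).** Half a year is 365 / 2 = 182.5, or about 182 days. Against 15 days the difference is at most 182 − 15 = 167 days. This is a worst case: an event just before a list is due would wait much less, and the SAE sentence sets a minimum frequency, so earlier listing is allowed though not required.

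**Does another provision close (c)?**

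- The 7- and 15-day limits say how fast an expedited report must be made. They do not decide which events enter that route.
- The prompt SAE report in 8.2.2 goes from investigator to sponsor and stops there.
- Section 8.1 tells the METC of a halt once the sponsor has decided on one. It does not report single events.
- The safety report (8.3) and the progress report (11.4) are annual, so they are slower than the half-yearly list.

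None of them gives case (c) a mandatory expedited route. Row (b) shows the reverse side of the same rule: an event that meets no seriousness criterion is expedited while (c) is not.

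**The case against.** The strongest reply is that *severe* is simply a slip for *serious*. Section 8.3 uses both words within one item, and 8.2.3 sets limits for fatal or life-threatening cases, which are seriousness criteria. That may well be the intention. But the legend directly above the rule gives *severe* a meaning of its own, and staff who follow the text will apply it. A slip would still need correcting.

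A second reply is that the people who must act are told anyway. This stands in large part. A reader might infer that seriousness triggers nothing, or that suspension under 8.1 would be delayed. The documents do not support either. The sponsor decides on suspension and hears of every SAE promptly, whatever its grade; seriousness also leads to the SAE listing and the annual summary table. Section 7.6 separately lists safety concerns as grounds for early termination. Only the step from sponsor to METC is slow.

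Three further inferences should also be resisted:

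- *The delay should be measured against 7 days.* That limit is for fatal or life-threatening cases, which would hardly be graded mild or moderate. The relevant contrast is 15 days.
- *All 75 patients (25 + 50) would be finished before the list is due.* The documents give no accrual rate, so this cannot be concluded; dividing 75 by 26 weeks merely assumes the answer.
- *The severe grade works poorly in catheterised inpatients, which widens the gap.* It could equally push grades upward and lead to more expediting.

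Finally, the risk is described as low and exposure is at most 24 hours, so such events should be rare. That limits how often the gap would matter but does not close it.

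**Conclusion.** Wrong as written. An ADE that meets a criterion of 8.2.2 but is graded mild or moderate has no mandatory expedited route to the METC. It can arrive up to about 6 months later instead of within 15 days. In practice this concerns prolonged hospitalisation, persistent or significant disability and other important medical events.

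The consequence is delayed independent review in a first-in-human trial with few other external checks. The conclusion rests on reading *severe* as the legend in 8.2.3 defines it, and on the 15-day limit applying to METC reports. No frequency can be given, because the documents offer no event rate. Sample size, endpoints and analysis are unaffected.

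**What to change.** Reconcile 8.2.2, 8.2.3 and 8.3 together:

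1. In 8.2.3, define a serious ADE as any ADE that meets a criterion of 8.2.2, whatever its intensity grade, and make it subject to expedited reporting under the timelines already there.
2. Exclude serious ADEs from the remaining ADEs that go on the half-yearly list.
3. In 8.2.2, exempt serious ADEs from the six-month line-listing sentence. Otherwise the same event would fall under two different sponsor rules.
4. Use *serious* consistently in 8.3.
5. Decide what happens to severe but non-serious ADEs, which are expedited now. Either keep them expedited, so that the trigger becomes serious or severe, or state openly that they would move to the half-yearly list. Simply swapping one word for the other would drop them without saying so.

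The cost is a wording amendment and possibly a few more expedited reports.
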